TITLE: **Neurochemical Effects of Omega-3 Fatty Acids in Adolescents at Risk for Mania**

UC-IRB#: 09-04-15-03

SPONSOR: Investigator Initiated with NIH/NIMH

FROM: Co-Principal Investigators: [name], MS, & [name]
Department of Psychiatry
University of Cincinnati College of Medicine
[name]
[name]

Sub-Investigators: [name]
[name]
[name]
[name]
[name]
[name]

II. RESEARCH PROTOCOL

A. Specific Aims: (1) To collect pilot data regarding the efficacy, safety, and tolerability of omega-3 fatty acid supplementation for the treatment of adolescents with active depressive symptoms and a high risk for developing mania (i.e. they have a bipolar parent and meet DSM-IV-TR criteria for major depressive disorder or depressive disorder not otherwise specified (NOS)). (2) To use proton magnetic resonance spectroscopy (¹H MRS) (i.e. prefrontal neurochemistry), plasma oxidation indices and cytokine concentrations, and red blood cell (RBC) omega-3 fatty acid levels to examine potential mediators of treatment response to omega-3 fatty acids in adolescents with a high risk for mania.

B. Background and Significance: The onset of bipolar disorder typically occurs during adolescence.¹⁻³ Family studies demonstrate that children with a bipolar parent have a 30% chance of developing a mood disorder, whereas children in whom both parents have a mood disorder (and at least one with bipolar disorder) have a 70% chance of developing a mood disorder.⁴ Offspring of bipolar parents therefore have an elevated risk of developing mood disorders compared with the general population.⁵⁻¹⁰ Moreover, when these offspring develop prominent mood symptoms or major depressive disorder, their risk of developing mania (and by definition bipolar disorder) increases even further.¹¹ However, antidepressants and other medications that are commonly used to treat these mood symptoms may accelerate the onset of mania or hypomania.¹²⁻¹⁸ Therefore, studies evaluating the efficacy, safety, and tolerability of potential treatments for mood symptoms in adolescents with a bipolar parent are necessary as an initial step toward establishing early intervention, and ultimately prevention, strategies for bipolar disorder.

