[name], Research Assistant Professor of Psychiatry and Biostatistics and Director of the Division of Quantitative Methods in the Department of Psychiatry UCCOM, has extensive expertise in the area of psychiatry and biostatistics. [name] will oversee all aspects related to database design and data management. He will lead the statistical analyses and complete exploratory post-hoc analyses. He will also assist in preparing manuscripts of the research findings.

E. Experimental Design and Methods:

Figure 1. Schedule of assessments for the 14-week trial

ASSESSMENT	SCREENING	BASELINE	WEEKS 1-11	WEEK 12 (TERMINATION)	WEEK 14 (FOLLOW-UP)
WASH-U KSADS	X	X			
Young Mania Rating Scale (YMRS)	X	X	X	X	X
Children's Depression Rating Scale-Revised (CDRS-R)	X	X	X	X	X
ADHD Rating Scale (ADHD Rating Scale-IV)	X	X	X	X	X
Clinical Global Impression-Severity (CGI-S)	X	X	X	X	X
Clinical Global Impression-Improvement (CGI-I)			X	X	X
Timeline Follow-Back	X	X	X	X	X
Child Behavior Checklist (CBCL)		X	X (Wk 4 & 8)	X	X
Teacher's Report Form (TRF)		X		X	
Children's Global Assessment Scale (CGAS)	X	X	X (Wk 4 & 8)	X	X
The Omega-3 Dietary Intake Questionnaire		X	X	X	
Columbia Suicide Severity Rating Scale (C-SSRS)	X	X	X	X	X
LIFE psychosocial functioning scales		X	X (Wk 4 & 8)	X	
Prior medical & treatment history, physical exam	X			X (physical exam)	
Vital signs	X	X	X	X	X
Urine toxicology screen & pregnancy test	X	X		X	
Serum laboratory tests (renal profile, complete blood count, liver & thyroid function tests, fasting lipid profile & glucose, and platelet function assay)	X			X	
Red blood cell omega-3 fatty acid levels	X			X	
Adverse events & adherence assessments	X	X	X	X	X
¹ H-MRS scan		X		X	
Total duration of appointment	2 hours	3 hours	1 hour	3 hours	1-2 hours

Figure 2. Study Design

DBPC=Double-blind placebo-controlled; SOC=Standard of Care Treatment

a. Methods and Procedures:

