omega-3 capsules contain 400 mg EPA and 200 mg DHA. The selected EPA/DHA ratio, or EDR, (EDR: 2.0) was based on prior controlled trials finding that EDRs closer to 2.0 (1.8-2.0), regardless of dose, were more effective in reducing depression symptom severity relative to placebo^{38,62-64} than were lower EDRs (0.25-1.4).⁶⁵⁻⁶⁸ We will administer one fixed dose of omega-3 fatty acids for the proposed trial. The omega-3 fatty acid dose, 1,800 mg/day (3 capsules/day: EPA: 1,200 mg/d, DHA: 600 mg/d), was selected because a lower fixed dose was found to be efficacious in pediatric (mean age=10 years) MDD patients (600 mg/d)³⁸ and a similar fixed dose was found to be efficacious in a primary prevention trial of adolescents (mean age=16 years) at high risk for psychosis (1,540 mg/d).⁶⁹ Additionally prior treatment studies⁷⁰⁻⁷² have found that comparable doses (1,000 - 2,160 mg/d), but not lower doses (200-482 mg/d), are required to increase RBC EPA+DHA content in young adults to a level thought to exert the greatest protection based on relative cross-national lifetime prevalence rates of MDD (U.S., 16.2% vs. Japan, <3%)^{73,74} and RBC EPA+DHA % of total fatty acids (U.S., 4.9% vs. Japan, 8.5%).^{75,76} The 12-week treatment duration was selected because 12-weeks of omega-3 supplementation has been found to normalize brain DHA concentrations in omega-3 fatty acid-deficient primates⁷⁷ and significantly reduce symptom severity in youth with MDD.³⁸

Nutritional Supplement Accountability and Subject Compliance: A record of all clinical supplies received, dispensed and destroyed will be maintained by the study staff. Study supplement supplies will be stored at controlled room temperature until time of dispensing to the study subject. Dispensing records will include a medication log for each subject detailing supplement dose received at each study visit. Study subjects will be asked to return all unused study supplement and the supplement bottle at each study visit. The amount of study supplement returned (if any) will be recorded by the study staff. Compliance will be determined by evaluating the dispensing records at the time a participant is discharged from the study.

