mood symptoms. It is possible for this prediction to be supported in the absence of a general association between treatment and mood symptoms (Prediction 1), which would suggest that these metabolic changes impact clinical outcome but are not induced by omega-3 fatty acids (i.e., they are a treatment-independent marker for clinical improvement). If both components of Prediction 4 are supported, it will be of further interest to assess the extent of mediation: If the direct (i.e., residual) treatment effect is not statistically significant, the data are consistent with *complete mediation* (i.e., the treatment effect on mood is fully accounted for by the intermediate effect on metabolite levels). If other effects of treatment on mood symptoms not specified by this model exist, the direct (i.e., residual) treatment effect may remain significant and the data would be said to support *partial mediation*. Path analysis⁸², which for linear models is a decomposition of the linear covariance matrix of the variables, will be used to analyze the fit of the proposed mediation model to our data. Path analysis can be thought of as an extension of linear regression to systems of simultaneous linear regression equations. This allows for the same variable to serve as an independent variable in some of the regressions and a dependent variable in others. In this study, changes in metabolite levels assume both roles: They are dependent variables in prediction 4(a) and independent variables in prediction 5(a). CDRS-R scores as well as other pilot mood measures will serve as the final outcome measures, with changes in metabolite levels as mediators and treatment group as an independent variable. Estimation of all the path coefficients, along with bootstrap computation of associated standard errors and significance levels (adjusted $\alpha=0.017$ to control for multiple testing) will be carried out using the SAS macros,⁷⁸ which are available for download at [http://www.comm.ohio-state.edu/ahayes/SPSS% 20programs/indirect.sas](http://www.comm.ohio-state.edu/ahayes/SPSS%20programs/indirect.sas). We also will examine the effect of metabolite changes on behavioral symptoms (ADHD-RS scores), functional ratings and the pilot mood burden scale on these models in a set of expanded path models. The Bayesian Information Criterion (BIC) will be used to assess the goodness of fit of different path models to the data. This model comparison statistics combines the likelihood of the data with a penalty term that adjusted for the number of parameters used to fit the data. This statistic can be used to rank the mediation model against simpler models where one or both of the components of Prediction 4 are assumed to be absent, or where these paths are supported with respect to some metabolites but not others. Another comparison of interest (though secondary to our aims) is to compare the full path model (which shows partial mediation, since a path representing residual treatment effect is included) to a complete mediation model which does not have a direct path from treatment to mood symptoms (implying that the correlation between treatment and mood symptoms, after accounting for metabolite levels, is zero). If both of the paths involving metabolite levels are null, but the correlation between treatment and mood symptoms is significant, the path model reduces to simple linear regression (i.e., a t-test, since the independent variable is binary). Comparison of overall model fit with BIC is important since a model in which the paths for predictions 4(a) and 4(b) fall somewhat close to significance, (e.g., $p=0.05$ for each path) may still give a better overall fit to the data than a model that omits both of these paths.

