
Prediction 5: The relationship between changes in RBC omega-3 fatty acid levels and changes in mood symptoms is mediated by metabolite changes. This prediction is similar to Prediction 4, but more precisely specifies the mechanism by which omega-3 fatty acids are hypothesized to influence mood symptoms. Specifically, changes in RBC omega-3 fatty acid levels (which are taken to be a surrogate for omega-3 levels in the brain) are predicted to be associated with changes in metabolite levels, which will in turn influence mood symptoms. These analyses will be performed in the subsample of subjects who are randomized to treatment with omega-3 fatty acids. Prediction 5(a) is that

increases in RBC omega-3 fatty acid levels will lead to decreases in Glu and mI levels and increases in NAA levels within VLPFC and ACC. While the mediation model of Prediction 4 specifies treatment assignment as the independent variable, in this set of models we treat RBC omega-3 levels within the omega-3 treated group as the predictor variable (although all subjects will receive the same nominal treatment they will display variation in their measured omega-3 levels due to differences in metabolism, diet and treatment compliance). Prediction 5(b) is that decreases in Glu and mI levels in VLPFC and ACC, and increases in NAA in VLPFC and ACC, will lead to decreases in mood symptoms. This component is the same as Prediction 4(b), but focused on the omega-3 treated group. While the metabolite level changes were dependent variables in Prediction 5(a), in Prediction 5(b) they are independent predictors of mood symptoms. As above, the covariance of these variables will be decomposed using path analysis, with $\alpha=0.017$ used to assess significance of individual paths, and BIC used to rank competing models (e.g., simplified models with one or more paths deleted).

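### No planned mediation model links randomised treatment to RBC omega-3 change, although Aim 2 names RBC omega-3 among the measures for examining mediators

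*Combined protocol and SAP*

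**What the plan says.** Specific Aims, Aim 2, lists MRS, plasma oxidation indices, cytokines and "red blood cell (RBC) omega-3 fatty acid levels to examine potential mediators of treatment response to omega-3 fatty acids".

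Section E.b, Data Analyses, then sets out two mediation models.

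- **Prediction 4** uses both arms. Mood scores are the outcome, "with changes in metabolite levels as mediators and treatment group as an independent variable". The mediators are Glu, mI and NAA; RBC omega-3 does not appear.
- **Prediction 5** brings RBC omega-3 in, with the metabolites again as mediators. On its role the plan says "in this set of models we treat RBC omega-3 levels within the omega-3 treated group as the predictor variable", and on the analysis set "These analyses will be performed in the subsample of subjects who are randomized to treatment with omega-3 fatty acids". Treated patients share one nominal dose, but the plan expects that "they will display variation in their measured omega-3 levels due to differences in metabolism, diet and treatment compliance". Individual paths are tested at alpha 0.017.

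The schedule of assessments has a row for "Red blood cell omega-3 fatty acid levels" at screening and week 12, with no restriction by arm. Under Estimated sample size, 30 patients are randomised per arm, and about 25% are expected to drop out or lack usable MRS data. No power or detectable effect is given for Prediction 5.

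**The concern.** A variable mediates a treatment effect if treatment moves it and it in turn moves the outcome. Examining RBC omega-3 in that role needs a model in which randomised treatment comes first and RBC change follows. Prediction 4 has the first element without the second; Prediction 5 has the second without the first.

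Within the omega-3 arm, RBC differences come from metabolism, diet and capsule-taking. A patient who takes capsules reliably may also eat, attend and recover differently. With no placebo counterpart, a positive Prediction 5 cannot be told apart from such an association, and at this sample size a null result would say little. At stake is how far the mechanistic results can be read. The efficacy comparison in Prediction 1 is not affected.

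**Working it through.** **1. The models side by side**

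| Analysis | Patients | Starting variable | Mediator | RBC omega-3 |
|---|---|---|---|---|
| Prediction 4 | both arms | treatment | Glu, mI, NAA | absent |
| Prediction 5 | omega-3 arm | RBC change | Glu, mI, NAA | predictor |
| Exploratory regressions | each arm, with interaction | omega-3 blood levels | none | association with symptom change |

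No row has treatment leading to RBC change leading to an outcome.

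**2. Precision of Prediction 5.** The plan states no figure to reproduce. Inputs from the plan are 30 per arm, 25% loss and alpha 0.017 (taken as two-sided). Then 30 × 0.75 = 22.5, so about 22 treated patients, and 60 × 0.75 = 45 in both arms. By Fisher's z, the smallest correlation with 80% power is r = tanh[(2.387 + 0.842)/√(n − 3)].

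- n = 22: tanh(3.228/√19) = 0.63
- n = 30 (no loss): tanh(3.228/√27) = 0.55
- n = 45: tanh(3.228/√42) = 0.46

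**3. The treatment-to-RBC link.** The plan predicts no RBC change and gives no SD. As an assumed scale I use the population contrast in Nutritional Supplement Dosing, "RBC EPA+DHA % of total fatty acids (U.S., 4.9% vs. Japan, 8.5"%: 8.5 − 4.9 = 3.6 points. With 22 per arm and an SD of 2.0 in both arms, the standard error is 2.0 × √(2/22) = 0.60, so a 3.6-point difference is about 6 standard errors. A rise of only 1.5 points would be about 2.5, close to the critical value of about 2.4.

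**4. The RBC-to-metabolite path.** Assumptions: 22 per arm, mean rise 3.6 on omega-3 and 0 on placebo, treated SD 1.0, 1.5 or 2.0, within-arm r = 0.4, alpha 0.017, and the whole treatment effect on metabolites running through RBC.

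With treatment in the model, the between-arm difference is absorbed by the treatment term, and the RBC slope rests on variation within the arms. Its standard error, relative to the omega-3 arm alone, is approximately √[s²/(s² + p²)], where s is the treated SD and p the placebo SD.

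- p = 0.7: √(1/1.49) = 0.82; √(2.25/2.74) = 0.91; √(4/4.49) = 0.94
- p = s: √(1/2) = 0.71

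Simulation (several thousand runs per case) agrees:

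| Model | s = 1.0 | s = 1.5 | s = 2.0 |
|---|---|---|---|
| Omega-3 arm only | about 0.30 | about 0.30 | about 0.30 |
| Both arms, treatment in model, p = 0.7 | 0.47 | 0.40 | 0.37 |
| Both arms, treatment in model, p = s | about 0.62 | about 0.62 | about 0.62 |
| Both arms, treatment omitted, p = 0.7 | 0.999 | 0.94 | 0.79 |

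Repeated runs put the second row between 0.36 and 0.48.

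**5. Share of RBC variance between arms.** With equal SDs it is (3.6²/4)/(3.6²/4 + SD²) = 3.24/(3.24 + SD²): 76% at SD 1.0, 59% at 1.5, 50% at 1.8 and 45% at 2.0.

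**The case against.** The strongest defence is that Prediction 5 is a deliberate and openly described choice. The plan contrasts its predictor with that of Prediction 4 and says where the variation comes from. Under Exploratory analyses it also argues that placebo response may work through other mechanisms, which is a reason to look within the treated arm. Dietary intake and adherence are measured. The exploratory regressions of omega-3 blood levels on symptom change in each arm come close to a placebo-arm check for mood. The randomisation paragraph speaks of RBC changes with supplementation versus placebo as something the design will allow to be assessed. All of this stands: Prediction 5 is a legitimate within-arm question. None of it is a mediation model with treatment leading to RBC change.

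Four stronger readings are tempting and are not supported.

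- **That Aim 2 promises a placebo-contrasted RBC model, which the plan then fails to run.** Aim 2 does not mention placebo and lists RBC alongside several other measures. The gap is that the plan contains no mediation model starting from treatment and passing through RBC.
- **That most of the RBC contrast is thrown away.** The randomised difference is lost to Prediction 5 by construction. Whether it is most of the RBC variation depends on an SD that the plan does not give; at 3.6 points and equal SDs, the break-even is 1.8. The 4.9% and 8.5% are national values, not a forecast for this trial.
- **That using both arms lifts power from 0.30 to between 0.79 and above 0.99.** This holds only if the direct treatment path is left out. RBC is then largely a proxy for arm, and the slope largely repeats Prediction 4(a).
- **That both arms remove the confounding.** With treatment in the model, the RBC slopes still rest on non-randomised variation.

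**Conclusion.** The point holds as a gap between Aim 2 and the planned models. RBC omega-3 is named for examining mediators, yet in the mediation models it appears only as a predictor among treated patients. That analysis has about 22 patients, a detectable correlation of about 0.63, and a non-randomised source of variation.

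Adding the placebo arm puts the treatment-to-RBC link on the randomised contrast and addresses Aim 2's mediation question for RBC. For the RBC-to-metabolite path the benefit is modest: from about 0.30 to 0.36-0.48, or about 0.62 with equal SDs. Those powers rest on the assumed 3.6-point rise, SDs and r = 0.4; the 0.63 rests only on the plan's own sample size, loss and alpha, with a two-sided test assumed. This is a pilot and the efficacy test is unaffected, so the change is worth making mainly because it is cheap. A stretch of text before section E is absent from the copy reviewed and could not be checked.

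**What to change.** 1. Add to Data Analyses a path model in all randomised patients: treatment to RBC change to metabolite change to mood change, with direct paths from treatment to metabolites and to mood. Use the bootstrap, path-level alpha and BIC comparison already planned.
2. Keep the omega-3-only model, labelled as a within-arm exposure-response analysis.
3. Repeat the RBC-to-metabolite and RBC-to-mood regressions in the placebo arm. An association there of similar size would point to diet or adherence-related behaviour rather than to the supplement.
4. State that the treatment-to-RBC path is randomised and that the RBC-to-metabolite and RBC-to-mood paths are not. If a version without the direct treatment paths is also shown, say that its RBC slope mostly reflects the arm difference.

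The cost is SAP wording and a few more model runs on RBC, MRS and mood data already scheduled in both arms. The downside is more results to report from a small pilot, with the later paths still open to confounding.

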A randomization schedule stratified by presence vs. absence of ADHD, presence vs. absence of concomitant stimulant treatment (within the ADHD group), and pre-pubescent vs. post pubescent (as determined by the Tanner Questionnaire with scores of 1-2 representing pre-pubescent and scores of 3-5 indicating post-pubescent) will be developed by the on-site biostatistician and will be used to assign omega-3 fatty acids (N=30) or placebo (N=30) treatment in a double-blind manner. We will stratify treatment assignment by some of the independently transmitted variables that contribute to the heterogeneity of at-risk adolescents (i.e. ADHD and concomitant use of stimulants) so that we will be able to assess the effects of these clinical factors on the neurophysiological and omega-3 fatty acid RBC level changes associated with supplementation of omega-3 fatty acids (vs. placebo) and examine potential neurophysiological markers of treatment response within clinically defined subgroups. We selected these variables for stratification because they may each affect outcome and treatment response.

Twelve-week Study Phase: During the 12-week DBPC phase subjects will participate in weekly research visits to assess symptom response and adverse side effects. Following the randomization visit, all visits will be scheduled weekly (or ≤ 10 days apart). The research visits will take approximately 1 hour; at these visits an experienced clinician will evaluate the patients for adverse effects and clinical response. Efficacy assessments will be obtained by a rater who is blind to side effects.

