- Any initiated psychotherapy within 2 months prior to the screening visit, or plans to initiate psychotherapy during study participation. Adolescents who present with their current depressive episode despite longer-term psychotherapy (i.e., >2 months) may be included. For participants who enter the study on psychotherapy, the type and frequency of therapy will remain constant during the study.

4. Inclusion of children, women, and minorities: The proposed study exclusively involves children ages 9-21 years old. As previously noted, we are not including children below age 9 years as it is not possible to control for age-related differences in brain development with the number of subjects we are proposing to study. We expect to enroll equal numbers of females and males in this study consistent with the epidemiology of offspring of parents with bipolar I disorder and of the local Cincinnati community (52.8% women and 47.2% men). Efforts will be made to have the study population reflect the ethnic distribution of the catchment area covered by the University of Cincinnati, which serves a population that is approximately 50% White, 45% African-American and 2% Asian, and 3% other racial groups, and the local Cincinnati area, which according to the 2000 Census report has a racial make-up of 53% White, 43% African American, 0.21% Native American, 1.55% Asian, 0.04% Pacific Islander, 0.63% from other races, and 1.68% from two or more races, and 1.28% of the population are Hispanic or Latino of any race.

NIH guidelines for the inclusion of females and minorities as subjects in clinical research will be followed. We will attempt to recruit equal numbers of each gender from each of the above racial groups. Most of our prior clinical trials achieved these gender, racial, and ethnic representations, and we expect the same for this study. We will analyze demographic data every four months and if we are failing to achieve these marks, we will increase our recruitment of the under-represented group by extending recruitment to other area clinics that include the under-represented group. There will be no exclusion of subjects based on gender, race, or ethnicity.

5. Study population source: Adolescents (ages 9-21 years) with a current DSM-IV-TR diagnosis of major depressive disorder (MDD) or Depressive Disorder NOS will be recruited from the University of Cincinnati BITREC “at-risk” cohort (n=140) of adolescent offspring of parents with bipolar I disorder.

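### Prediction 5 has no age or pubertal covariate: within the omega-3 arm, the path from RBC omega-3 to metabolites is confounded if age relates to both 12-week changes

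*Combined protocol and SAP*

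**What the plan says.** All references are to the Combined protocol and SAP.

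- **Analysis set and exposure (II.E.b, Prediction 5).** "These analyses will be performed in the subsample of subjects who are randomized to treatment with omega-3 fatty acids". There, "we treat RBC omega-3 levels within the omega-3 treated group as the predictor variable".
- **Source of exposure variation (same section).** Of the treated subjects: "they will display variation in their measured omega-3 levels due to differences in metabolism, diet and treatment compliance".
- **Model (same section).** "As above, the covariance of these variables will be decomposed using path analysis". The variables named are RBC omega-3, metabolite changes and mood symptoms; no covariate is listed. An alpha of 0.017 is "used to assess significance of individual paths, and BIC used to rank competing models". The direction is stated causally: rises in RBC omega-3 are predicted to bring about the metabolite changes.
- **Dose and age (II.E.a, Nutritional Supplement Dosing; II.F.3).** "We will administer one fixed dose of omega-3 fatty acids for the proposed trial", and eligibility runs from 9 to 21 years.
- **Age and the brain (II.F.4).** Children under 9 are left out because "it is not possible to control for age-related differences in brain development with the number of subjects we are proposing to study".
- **Pubertal stage (II.E.a, Screening, Baseline, & Randomization).** Tanner stage (1-2 versus 3-5) is a randomisation stratum, alongside ADHD and stimulant use. Of the stratifiers the protocol says "We selected these variables for stratification because they may each affect outcome and treatment response".

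**The concern.** Randomisation and stratification balance the two arms against each other. They give no protection to a comparison made inside one arm. In Prediction 5, patients with large and small RBC responses are compared as they happen to fall, and anything that drives both the RBC response and the metabolite change will appear as a path between them.

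Age is the obvious candidate. The same daily amount goes to a 9-year-old and a 21-year-old, so the RBC response may vary with age. The outcome is a brain measure in a population still maturing. If both links exist, part or all of path 5(a) is a developmental correlation. With the opposite sign, the same mechanism could hide a real path.

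What is at stake is the reading of 5(a), and through it the biological explanation that Prediction 5 is meant to sharpen. The randomised comparison in Prediction 1 is not affected.

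**Working it through.** **1. The plan's own figure.** With three tests, Bonferroni gives 0.05/3 = 0.0167 and Sidak gives 1 - 0.95^(1/3) = 0.01695; both round to 0.017. The count of three is inferred from the three metabolites (Glu, mI, NAA). The 0.017 is taken as two-sided, which the plan does not state.

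**2. Sample size.** 30 patients in the arm, less 25% who discontinue or lack usable MRS data (II.F.2): 30 x 0.75 = 22.5, taken as 22.

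**3. Is age brought in elsewhere?**
- Prediction 1 names study week and treatment group, then promises to look at other covariates, specifying ADHD, anxiety disorders and stimulants.
- Prediction 2 explicitly carries covariates over from above; Prediction 5 carries over only the path-analysis method.
- The exploratory analyses of RBC and metabolite change name nicotine, illness duration, and behavioural, functional and mood measures.

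None of these names age or pubertal stage.

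**4. Form of the bias.** If age is the only common cause and RBC has no true effect, the correlation between RBC change and metabolite change equals the product of their two correlations with age. It is 0.3 x 0.3 = 0.09, or 0.5 x 0.5 = 0.25, and zero if either link is zero. At n = 22 the smallest significant correlation is t/sqrt(df + t^2) with t = 2.603 on 20 df, which is 0.503.

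**5. False-positive rate of one 5(a) path.** Simulation, 40,000 runs per row, no true RBC effect, two-sided alpha 0.017. The correlations are assumptions; none is in the documents.

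| Age-RBC / age-metabolite | Spurious r | n=22, no age | n=22, age included | n=30, no age |
|---|---|---|---|---|
| 0 / 0 | 0 | 1.8% | 1.8% | 1.7% |
| 0.3 / 0.3 | 0.09 | 2.4% | 1.6% | 3.0% |
| 0.4 / 0.4 | 0.16 | 4.6% | 1.7% | 6.2% |
| 0.5 / 0.5 | 0.25 | 10.1% | 1.8% | 14.4% |
| 0.5 / 0 | 0 | 1.7% | 1.7% | 1.7% |

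**6. Both paths together.** Adding a mood variable (n = 22, alpha 0.017 for each path, 5(b) tested given RBC), with no true effect of RBC or metabolite and an age-mood correlation from 0 to 0.5, both paths are significant in about 0.6% of runs or fewer per metabolite. This holds even with 0.5/0.5 for the other two correlations. If the metabolite truly affects mood (correlation 0.5, no separate age-mood link), the joint rate at 0.5/0.5 is about 4%, still well below the 10% for 5(a) alone.

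**7. Cost of adding age at n = 22.** The smallest significant (partial) correlation rises from 0.503 to 0.515. Power for a true partial correlation of 0.5 falls from 52% to 49%, and for 0.6 from 76% to 73%.

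**The case against.** The strongest reply is that the size rests on correlations the documents do not supply. Prediction 5 largely concerns 12-week changes, which remove stable age differences in level. Age must therefore relate to the change in both quantities, and the remark in II.F.4 says nothing about 12-week change; it explains the lower age limit. This stands. It is why the conclusion is conditional and why 2-3% is as admissible as 10%. It is weakened a little because the section also calls the predictor RBC levels, and a level would be more exposed to age.

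Second, a reader might infer that a significant 5(a) path would by itself be taken as proof of mechanism. The documents do not support that. Prediction 4 requires both an exposure-metabolite and a metabolite-mood association for mediation, and Prediction 5 follows it. The concern is with 5(a) as a reported result.

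Third, a reader might add up six paths (three metabolites, two regions) into an alarming overall error rate. At 0.017 each, six independent tests already give 1 - 0.983^6 = 9.8% without any confounding. The excess from age would further depend on every metabolite sharing the same assumed correlation. Since Glu and mI are predicted to fall and NAA to rise, a confounder acting in one direction would push some paths against prediction.

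Fourth, body size might seem an equal confounder. Acting only through dose per kilogram, it is genuine exposure variation, the very signal Prediction 5 uses. The schedule of assessments does not name weight.

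Fifth, metabolism in the plan's list could include age effects, the sentence before the stratification quote singles out ADHD and stimulants, and some text preceding section E is not in the public copy, so the covariates referred to in Prediction 1 cannot be fully traced. These points soften the evidence; none puts age into the model. Nor does the pilot aim remove the value of a covariate that is already collected.

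**Conclusion.** The concern holds in a conditional form. Prediction 5 is a non-randomised, within-arm analysis, worded causally, with no age or pubertal covariate in a population aged 9 to 21 on one fixed dose. If age correlates with both the RBC change and the metabolite change, 5(a) is confounded.

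The documents do not show that these links exist or how strong they are. At n = 22 the inflation is slight if both are near 0.3, material if both are near 0.5 (about 10% against 1.7%), and nil if either is absent. These figures assume linear effects, age as the only common cause and a two-sided 0.017.

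A reader might infer that the plan will often produce false mediation claims, or that the fixed dose is itself at fault. Neither follows: the two-path requirement makes false mediation much rarer than a false 5(a), and this point concerns the analysis only.

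**What to change.** In Prediction 5, specify baseline age (or Tanner stage) as a covariate in both the metabolite equation and the mood equation of every path model. Make this the main version, report the unadjusted model second, and describe the RBC path as an adjusted association. Choose between age and Tanner stage before the data are seen. In the same edit, reconcile whether the predictor is the RBC level or its change.

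Body weight should not be offered as a substitute for age, and nothing here requires baseline RBC omega-3 as a further covariate.

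The cost is SAP wording and about one degree of freedom out of 22 patients, with slightly wider intervals and the small loss of power shown above. No new data are needed, since age and Tanner stage are already obtained for eligibility and stratification.
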